12.1.1 Efficacy analysis set

A randomized subject will be considered valid for per protocol efficacy analysis if the subject:

- has received study medication according to the study protocol
- has been subjected to a RIPC or a sham procedure according to the study protocol
- has undergone PCI within one hour after RIPC or sham procedure
- has provided a valid blood sample for cTnI determination at 24 hours post-pCI

12.1.2 Safety analysis set

A randomized subject will be considered valid for safety analysis if at least 1 dose of study medication has been administered.

12.2 Methods of statistical analyses

The efficacy analysis will be performed in the population of subjects valid for safety analysis.

The statistical assessment of the primary outcome measure (post-procedural cTnI) will be performed using ANCOVA (analysis of covariance), with post-procedural cTnI as a dependent variable, -ticagrelor/clopidogrel treatment and –RIPC/no RIPC as fixed factors and pre-procedural cTnI as a covariate. If not mentioned otherwise, all statistical tests will be performed tow-sided with a type I error rate of 5% and 95% confidence intervals (two-sided) will be given.

The statistical assessment of the secondary outcome measures (pain score, and ST-segment deviation) will be performed using ANOVA (analysis of variance). The ANOVA tests the null hypothesis that samples in two or more groups are drawn from populations with the same mean values. If the ANOVA test is statistically significant, pairwise comparison of subgroups will be performed with the Tukey-Kramer test. If not mentioned otherwise, all statistical tests will be performed tow-sided with a type I error rate of 5% and 95% confidence intervals (two-sided) will be given.

The safety analysis will be performed in the population of subjects valid for safety analysis.

The incidence of the composite of major and non-major bleeding according to the TIMI criteria and the incidence of major bleeding will be tabulated and further analyzed using Fisher's exact test. Fisher's exact test is a significance test for a 2x2 table. This test evaluates all distribution probabilities for a 2 x 2 table and produces an exact probability for a given set of observed frequencies. The null hypothesis is that the row and column variables are unrelated, or that there is no difference in the respective proportions. If not mentioned otherwise, all statistical tests will be performed two-sided with a type I error rate of 5% and 95% confidence intervals (two-sided) will be given.

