1.2 Research hypothesis

We will study the effect of ticagrelor on the reduction of PMI and the incidence of post-PCI MI with the use of RIPC. Our primary research hypothesis is that treatment with ticagrelor will potentiate the effects of RIPC and, therefore, reduce PMI, as assessed by post-procedural troponin release.

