1.3 Rationale for conducting this study

Our research group has significant experience in utilizing RIPC for the prevention of periprocedural myocardial injury (PMI) in the setting of PCI.⁸ We have recently demonstrated in a randomized clinical trial that RIPC can effectively reduce PMI and post-PCI myocardial infarction in the setting of ad hoc PCI for stable coronary artery disease.¹⁹ Furthermore, we have recently published a meta-analysis, providing compelling evidence for the beneficial effects of RIPC in the setting of elective PCI.²⁰

In this setting we have designed a randomized clinical trial to assess the effect of ticagrelor on the reduction of PMI and the incidence of post-PCI MI with the use of RIPC.

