2. STUDY OBJECTIVES

2.1 Primary objective

The primary objective of this study is to demonstrate superior efficacy of a combination of ticagrelor and RIPC in the reduction of PMI compared to a clopidogrel-RIPC combination or ticagrelor alone, by evaluating post-procedural cardiac Troponin I (cTnI) levels, defined as cTnI at 24 hours post-PCI.

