12.3 Determination of sample size

According to our previous research¹⁹ and other available studies on the subject²⁰ we have assumed post-procedural cTnI to be approximately 0.10ng/mL in the RPC group (0.08ng/mL for the ticagrelor group and 0.12 for the clopidogrel group) and approximately 0.19ng/mL for the control group (0.14ng/mL for the ticagrelor group and 0.24 for the clopidogrel group), with a standard deviation of 0.20 for both groups. According to our previous experience the correlation coefficient between preprocedural and postprocedural cTnI is approximately 0.7. Based on previously published methods,^{28,29} we have estimated a sample size of 152 patients (38 patients for each group) to achieve a statistical power of 80% with $\alpha=0.05$, incorporating a dropout rate of 15% (pci failure, revoked consent, etc.)

Statistical analyses have been performed using IBM SPSS Statistics v21, (IBM Corporation), and Power Analysis v1.4 (A&X Analytics).

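### The primary objective, the primary ANCOVA and the effect behind the 80% power do not match, and no decisive test is named

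*Combined protocol and SAP*

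**What the plan says.** Section 2.1 sets the primary aim: to "demonstrate superior efficacy of a combination of ticagrelor and RIPC in the reduction of PMI compared to a clopidogrel-RIPC combination or ticagrelor alone", judged on cTnI at 24 hours. Section 1.2 gives the hypothesis that "treatment with ticagrelor will potentiate the effects of RIPC and, therefore, reduce PMI, as assessed by post-procedural troponin release". Section 1.3 says the trial was designed to "assess the effect of ticagrelor on the reduction of PMI and the incidence of post-PCI MI with the use of RIPC".

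Section 12.2 analyses post-procedural cTnI by ANCOVA with ticagrelor/clopidogrel and "RIPC/no RIPC as fixed factors and pre-procedural cTnI as a covariate". Nothing further is named for this outcome. A pairwise step does appear, under which "pairwise comparison of subgroups will be performed with the Tukey-Kramer test", but only in the paragraph on pain score and ST-segment deviation and only after a significant ANOVA.

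Section 12.3 assumes cTnI means with RIPC of "0.08ng/mL for the ticagrelor group and 0.12 for the clopidogrel group", and without RIPC of "0.14ng/mL for the ticagrelor group and 0.24 for the clopidogrel group". The SD is 0.20 and the pre/post correlation about 0.7. It then states "we have estimated a sample size of 152 patients (38 patients for each group) to achieve a statistical power of 80" per cent at alpha 0.05, with 15% dropout included. The comparison that has this power is not identified.

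**The concern.** Sections 1.2, 1.3 and 2.1 ask about one cell of the 2×2 design, the combination, against named neighbouring cells, or about whether one treatment strengthens the other. The factor effects in Section 12.2 average over the other factor. The two questions have the same answer only if there is no interaction.

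Three things are at stake.

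- A significant ticagrelor or RIPC factor effect could be reported as meeting Section 2.1 although the combination has been shown better than neither named comparator.
- The word 'or' leaves open whether one or both comparisons must succeed, so success could be defined after the data are seen.
- A reader will take the 80% as the power for the stated objective.

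**Working it through.** **Inputs (Section 12.3).** Means in ng/mL: ticagrelor+RIPC 0.08, clopidogrel+RIPC 0.12, ticagrelor alone 0.14, clopidogrel alone 0.24. SD 0.20, r = 0.7, two-sided alpha 0.05, 38 per cell, 15% dropout. Assumed here: equal SD and r in all cells, and normal errors.

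**Adjusted SD.** 0.20 × √(1 − 0.7²) = 0.1428.

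**Reproducing 152.** The ticagrelor main effect is (0.12 + 0.24)/2 − (0.08 + 0.14)/2 = 0.18 − 0.11 = 0.07. Patients per arm = 2 × [0.1428 × (1.960 + 0.842)/0.07]² = 65.4, so 66 per arm and 33 per cell. Then 33 × 1.15 = 37.95, so 38 per cell and 152 in total. The RIPC main effect (0.19 − 0.10 = 0.09) gives only 92 to 95 patients with adjustment.

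**Additivity of the plan's means.** RIPC effect on ticagrelor: 0.14 − 0.08 = 0.06. On clopidogrel: 0.24 − 0.12 = 0.12. Rounding of the means does not remove the gap: at most 0.145 − 0.075 = 0.07 on ticagrelor, and at least 0.235 − 0.125 = 0.11 on clopidogrel. On the difference scale, which is the scale of this ANCOVA, the assumed RIPC effect is smaller with ticagrelor.

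**Standard errors with n per cell.** Cell contrast: 0.1428 × √(2/n). Main effect: 0.1428 × √(1/n). Interaction: 0.1428 × √(4/n). After dropout, 38 × 0.85 = 32.3, so n = 32. As an example, for 0.06 at n = 32 the SE is 0.0357, so z = 1.680 and power ≈ Φ(1.680 − 1.960) = 0.39.

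**Power on the plan's means.** The figures come from simulated cell means and residual variances, with t tests on 4n − 5 df.

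| Test | Difference | n = 32 | n = 38 |
|---|---|---|---|
| Ticagrelor main effect | 0.07 | 0.785 | 0.852 |
| Combination v clopidogrel+RIPC | 0.04 | 0.198 | 0.228 |
| Combination v ticagrelor alone | 0.06 | 0.385 | 0.444 |
| At least one contrast, unadjusted | | 0.449 | 0.507 |
| At least one, Hochberg / Dunnett | | 0.341 / 0.344 | 0.398 / 0.401 |
| Both contrasts | | 0.134 | 0.165 |
| Interaction | 0.06 | 0.218 | 0.251 |

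At 33 per cell, the normal approximation gives 80.4% for the ticagrelor main effect.

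**Discordance.** In the same simulation at n = 32, the ticagrelor main effect is significant with neither named contrast significant in about 42% of trials.

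**Sensitivity to r (n = 32).** For r from 0.6 to 0.8, at least one contrast unadjusted runs from 38% to 57%, and both from 10% to 20%.

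**Strictly additive model (no interaction fitted), n = 32.** The difference between the combination and clopidogrel+RIPC is then estimated by the ticagrelor main effect, and the difference from ticagrelor alone by the RIPC main effect. Power is 78% and 94% respectively, 74% for both and 99% for either. On the plan's means, however, these estimates centre on 0.07 and 0.09, where the named contrasts are 0.04 and 0.06. Each overstates its contrast by 0.03.

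**The case against.** The strongest defence is that this is a declared 2×2 factorial with two successive 1:1 allocations, for which two fixed factors are a normal analysis. The sample size reproduces exactly from the ticagrelor main effect, so the loose part may be the wording of Section 2.1 and not the analysis. This stands as an account of how the mismatch may have arisen, and it is why restating the objective is a full alternative below. It does not remove the mismatch.

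A reader might go further than the documents allow in five ways.

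- *That 152 is an arithmetic error.* It is not; it fits the ticagrelor main effect.
- *That Section 12.2 excludes an interaction, or cannot test the objective at all.* It excludes nothing, and main effects do answer Section 2.1 if the effects are additive. The fault is that no term or contrast is named and none is made decisive.
- *That power is below 80% on every reading.* The low figures are for separately estimated contrasts. An additive model gives 99% for either, and 74% for both at 32 per cell (82% at 38), at the price of the bias shown above.
- *That an unadjusted four-group F test explains 152 equally well.* It also needs 33 per cell, but it ignores the stated r = 0.7 and the cited ANCOVA sample-size formula. With the adjustment it needs only about 17 or 18 per cell.
- *That the assumed means contradict potentiation on every scale.* On the ratio scale (0.08/0.14 = 0.57 v 0.12/0.24 = 0.50), rounding leaves the direction open: 0.075/0.145 = 0.517 against 0.125/0.235 = 0.532.

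**Conclusion.** The point holds: objective, model and powered effect are not aligned, and this must be fixed before analysis. The 80% belongs, as best it can be reconstructed, to the ticagrelor main effect (78–80% after dropout, 85% with all 38 per cell). The comparisons that Section 2.1 names, estimated separately, have 13% to 45% depending on how 'or' is read, and 13% to 51% if the full 38 per cell is also considered.

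These are nominal normal-theory values. The plan's inputs are labelled approximate, and an SD of 0.20 beside means of 0.08 to 0.24 for a non-negative assay implies marked skew. The exact percentages should therefore not be pressed. The gap between the main effect and the named contrasts is large enough not to depend on them, and it persists for r from 0.6 to 0.8.

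**What to change.** Two options of equal standing; the choice is the sponsor's.

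**(a) Keep Section 2.1.** In Section 12.2, fit the ticagrelor × RIPC term and name as primary the two baseline-adjusted contrasts: combination v clopidogrel+RIPC, and combination v ticagrelor alone. State whether both are required (each at two-sided 5%, no alpha split) or either suffices (with Hochberg or Dunnett). Without adjustment, two such tests sharing an arm have a family-wise error of about 9.1%. In Section 12.3, name the effect behind 152 and restate the power of the contrasts at 152 patients under the chosen rule.

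**(b) Restate Sections 1.2 and 2.1** so that the primary question is the ticagrelor main effect, which 152 supports. Name that effect in Sections 12.2 and 12.3. Report the interaction with its 95% CI, and the cell contrasts, as supportive.

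Under either option, name the scale on which potentiation is judged, and make no claim of combination superiority or potentiation from main effects alone, without the interaction and contrasts beside them.

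**Cost.** Wording, a few lines of code, and an amendment needing prior approval under Section 8.4. Option (a) also means a less favourable stated power. No new data, visits or patients are needed. Resizing is optional: for information, 80% power on the plan's means needs about 99 evaluable per cell for at least one contrast with Hochberg or Dunnett (4 × 99/0.85 ≈ 466 patients), or about 203 per cell for both (4 × 203/0.85 ≈ 956).

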3. STUDY PLAN AND PROCEDURES

3.1 Overall study design and flow chart

The TRIP study will be a randomized, assessor-blind, active comparator-controlled, clinical trial using a 2×2 factorial design, with 1:1 patient allocation to ticagrelor or clopidogrel and within each treatment a 1:1 allocation to RIPC or control.

According to the study plan, patients who are referred for coronary angiography or NSTEMI-ACS may be screened for randomization.

	Day 1/ Screening	Day 2	Day 3	Day 30 (±5days)
Informed consent form	x			
Inclusion criteria	x			
Exclusion criteria	x	x	x	

Medical history	X			X
Concomitant disease	X			X
Concomitant medication	X	X	X	X
Physical examination (vital signs)	X	X	X	X
ECG	X	X		
Local laboratory values	X	X	X	
Randomization	X	X		
Treatment initiation	X			
RIPC		X		
Coronary angiography assessment		X		
PCI		X		

[figure not shown]
Day 1 of the study is defined as the day of randomization to ticagrelor versus clopidogrel. This should be chosen by the investigator to be the day before the scheduled PCI procedure.

Day 2 of the study is defined as the day of randomization to RIPC or control and subsequent (within 1 hour) coronary angiography and PCI.

In patients already treated with clopidogrel for 3 to 7 days, actions performed on Day 1 and Day 2 may be combined into a single day provided that;

- a. Twenty four hours have elapsed between the last dose of clopidogrel and the randomization to the ticagrelor or clopidogrel group, and
- b. There is sufficient time (2-4 hours) between the randomization and subsequent intake of clopidogrel or ticagrelor and the 2nd randomization to the RIPC or control group.

If for unforeseen reasons, PCI is not conducted within the prespecified timeframe the patient should be withdrawn from the study.

* In case of a patient already on clopidogrel for 3-7 days, ticagrelor loading dose is administered on the day of the procedure (24 hours after the last clopidogrel dose), and no 2nd ticagrelor dose is administered. ** In case of a patient already on clopidogrel for 3-7 days, no loading dose of clopidogrel is administered, but the patient ideally receives 75mg clopidogrel 2-3 hours before the procedure.

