5.1.1 Procedures for randomization

The TRIP study will be a randomized, assessor-blind, active comparator-controlled, clinical trial using a 2×2 factorial design, with 1:1 patient allocation to ticagrelor or clopidogrel and within each treatment a 1:1 allocation to RIPC or control. Patient randomization in the ticagrelor and the clopidogrel group will take place using sealed, opaque envelopes containing a computer-generated randomization scheme. Using a similar procedure, patients will be randomly assigned to RIPC or no RIPC within 1 hour before the procedure.

5.2 Procedures for handling subjects incorrectly enrolled or randomized or initiated on investigational product

Subjects who fail to meet the inclusion and exclusion criteria are defined as screening failures. The investigator will maintain a Screening Log which includes screen failures. The log will document the subject number, subject initials, demographics and the reason(s) for excluding the patient from the study. This log will be kept in the Investigator's Study File. It will be used to determine systematic bias in selection of patients for entry into the study.

Subjects who withdraw or are withdrawn from the study following randomization, before investigational product initiation should:

- Have the reason(s) for their withdrawal recorded

Subjects who withdraw or are withdrawn from the study following randomization and investigational product initiation should:

- Have the reason(s) for their withdrawal recorded
- Be asked about the presence of any AEs and if so should be followed up by regular scheduled visits, telephone contact, correspondence or home visits until satisfactory clinical resolution of AEs is achieved.
- Be seen by an investigator and all final assessments will be performed and recorded in the termination page of CRF.
- Have at least one follow-up contact for safety evaluation during the 30 days following the last dose of study treatment.
- In the event of pregnancy, the subject should be monitored until conclusion of the pregnancy and the outcome of pregnancy reported.
- Have study treatment returned (according to accountability practices)

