6.2 Data collection at enrolment and follow-up

Screening (in most cases expected to be the same day with first randomization-Day1)

During this period the investigator will evaluate and record

- Indication for coronary angiography or PCI (stable CAD, NSTEMI-ACS)
- Demographics (age, gender, height, weight, body mass index)
- History of risk factors for cardiovascular disease (Diabetes mellitus, dyslipidemia, hypertension, smoking)
- Medical history including history of previous MI, previous PCI, previous CABG, New York Heart Association Class, Canadian Cardiology Society Angina Class
- Prior and concomitant medication
- Physical examination with vital signs (heart rate, blood pressure)
- Electrocardiogram
- Local laboratory values (hemoglobin, complete blood count including platelet count, serum creatinine, AST, ALT, INR, cardiac Troponin I)

Day 2 - Pre-procedural assessment

- Physical examination with vital signs (heart rate, blood pressure). At this time signs and symptoms of bleeding should be specifically examined.
- Local laboratory values (hemoglobin, complete blood count including platelet count, serum creatinine, AST, ALT, INR, cardiac Troponin I)

In the case of patients already on clopidogrel there will be one combined assessment for screening and pre-procedurally.

Day 2 - Preconditioning

- The timing of the last cycle of RIPC in relation to subsequent PCI should be specifically recorded

Day 2 - Peri-procedural

- Angiographic parameters (number of diseased vessels, target vessel, jeopardy score, rentrop score, American heart association lesion type, stenosis severity, acute gain, timi flow score)
- Procedural parameters (access site, stent length, type of stent used, screen time, radiation dose, contrast dose, number of predilations, predilation time, number of postdilations, postdilation time)
- Complications (jailed side branch, dissection)
- ST-segment deviation during balloon occlusion will be monitored as a secondary efficacy variable. It will be defined as the absolute value of ST-segment deviation at 60-80ms after the J-point in mm at the beginning of coronary angiography minus ST-segment deviation at 60-80ms after the J-point in mm during balloon occlusion.

Day 2 - Post-procedural

- Physical examination with vital signs (heart rate, blood pressure). At this time signs and symptoms of access site bleeding should be specifically examined.
- Electrocardiogram

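### Prior clopidogrel use is recorded before randomisation and changes the patient's course, but is not a covariate in the primary or secondary models: an optional, almost free improvement

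*Combined protocol and SAP*

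**What the plan says.** - **Primary model (section 12.2).** Post-procedural cTnI is analysed by ANCOVA with ticagrelor/clopidogrel and "RIPC/no RIPC as fixed factors and pre-procedural cTnI as a covariate". No other baseline term is named.
- **Secondary models (section 12.2).** Pain score and ST-segment deviation are analysed by ANOVA, with no covariate named.
- **Randomisation (section 5.1.1).** Allocation uses "sealed, opaque envelopes containing a computer-generated randomization scheme". No stratification factor is given for either randomisation.
- **What is recorded at screening (section 6.2).** The list includes prior and concomitant medication, and "Indication for coronary angiography or PCI (stable CAD, NSTEMI-ACS").
- **What prior clopidogrel changes.** Section 3.1 (repeated in 5.1) allows a same-day course under two timing conditions, in a sentence that opens "In patients already treated with clopidogrel for 3 to 7 days, actions performed on Day 1 and Day 2 may be combined into a single". The footnotes to section 3.1, and section 5.4.2 for the clopidogrel arm, give these patients a different regimen before PCI. Section 6.2 gives patients already on clopidogrel one combined screening and pre-procedural assessment.
- **Sample size (section 12.3).** 152 patients, "to achieve a statistical power of 80"%, with a pre/post cTnI correlation of 0.7 and 15% dropout.

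**The concern.** A factor fixed before the first randomisation, already in the case report form, and tied to a different route to PCI is a natural candidate for adjustment. It may also bear on the one covariate the model does have. Patients not on clopidogrel start study drug on Day 1 and have a separate cTnI on Day 2. Patients already on clopidogrel have a single combined assessment. Pre-procedural cTnI can therefore stand at a different point relative to study drug in the two groups, while the model fits one common relation to it. Adjusting for cTnI alone may not absorb whatever prior clopidogrel contributes.

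Two modest things are at stake. If the factor is prognostic, its variance stays in the residual of a trial whose drug effect is sized with no spare power. And with about 65 evaluable patients per drug arm and no stratification, the arms can differ by chance in the proportion already on clopidogrel, with no term in the model to allow for it.

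**Working it through.** **Inputs from section 12.3.** Cell means with RIPC: "0.08ng/mL for the ticagrelor group and 0.12 for the clopidogrel group"; without RIPC: 0.14 and 0.24 ng/mL. SD 0.20, correlation 0.7, 15% dropout, N = 152. Section 12.2 sets the tests two-sided at 5%.

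**Step 1: reproduce the plan's figure.**
- Drug main effect: (0.12 + 0.24)/2 − (0.08 + 0.14)/2 = 0.18 − 0.11 = 0.07 ng/mL.
- Residual variance after cTnI: 0.20² × (1 − 0.7²) = 0.0204, so the residual SD is 0.143.
- Per arm: 2 × (1.960 + 0.842)² × 0.0204/0.07² = 65.4, rounded up to 66; total 132.
- 132 × 1.15 = 151.8, giving 152. The stated N reproduces.
- Power at 132 evaluable is 80.4%; without the cTnI covariate it would be 52.0%. The planned covariate already does most of the work.
- The RIPC main effect (0.19 − 0.10 = 0.09) needs only 80 evaluable, so the drug effect is the contrast with no slack.

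**Step 2: power if 15% are lost.** 152 × 0.85 = 129.2, or 64.6 per arm. SE = 0.1428 × √(2/64.6) = 0.0251. Power = Φ(0.07/0.0251 − 1.96) = 79.5%.

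**Step 3: power with prior clopidogrel added.** The documents give neither the prevalence *s* nor the shift *D* in cTnI that remains after adjustment for baseline cTnI. Assumed: *s* = 30–50%, *D* = 0.05–0.10 ng/mL. Partial R² = s(1 − s)D²/0.0204, and the SE is multiplied by √(1 − R²).

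| s | D (ng/mL) | Partial R² | Power at 129 |
|---|---|---|---|
| any | 0 | 0 | 79.5% |
| 30% | 0.05 | 0.026 | 80.6% |
| 50% | 0.05 | 0.031 | 80.8% |
| 30% | 0.10 | 0.103 | 83.7% |
| 50% | 0.10 | 0.123 | 84.5% |

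The gain is about 1 to 5 points. If D = 0 the price is one degree of freedom; even two cost only about 0.01 percentage points of power.

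**Step 4: chance imbalance between drug arms.** SD = √(2s(1 − s)/64.6), which is 8.1 points at 30% and 8.8 points at 50%. The 95% range is therefore about ±16 to ±17 points. At the edge of that range the drug estimate moves by 0.158 × 0.05 = 0.008 up to 0.172 × 0.10 = 0.017 ng/mL, or 11% to 25% of 0.07. A one-SD imbalance moves it about half as much (0.004 to 0.009 ng/mL). Against the SE of 0.025, the edge-of-range shift is 0.3 to 0.7 of one standard error.

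**The case against.** The strongest reply is that nothing here is wrong. The plan prespecifies an ANCOVA on the baseline value of its outcome, sizes the trial on that model and reaches its own 80%. Leaving out a prognostic covariate does not bias a randomised comparison or invalidate the 5% test, and the confidence interval already allows for chance imbalance. No section promises stratification or further adjustment. All of this stands.

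The benefit is also conditional. The documents show no association between prior clopidogrel and 24-hour cTnI given baseline cTnI, and the assumed shift is large: 0.7 to 1.4 times the planned drug effect. Any part that acts through baseline troponin is already adjusted for, and exclusion criterion 3 limits baseline cTnI. This stands too, and is why the gain can be stated only as a range that starts at zero.

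Two further objections stand in part:
- The altered course differs by drug arm, so an additive yes/no term captures a prognostic difference and not a difference in treatment effect. It still does what baseline adjustment is for.
- ST deviation is defined as a change from the start of angiography, so it carries its own baseline value. That does not cover prior clopidogrel, and pain has no baseline value. No size can be given for either outcome.

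A reader might extend the point to indication, since section 6.2 records it and section 4 names both stable CAD and NSTEMI-ACS. The documents do not support treating it alike. Indication changes no schedule, dosing or endpoint timing before the 24-hour sample; its one stated role is the duration of dual antiplatelet treatment after ticagrelor is stopped (section 5.7.1). Inclusion criterion 3 in section 4.1 lists NSTEMI-ACS only; read literally, indication does not vary.

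**Conclusion.** The point holds as an optional improvement, limited to prior clopidogrel. The factor is known before the first randomisation, changes the patient's course and appears in no model. Adjusting for it would add roughly 1 to 5 points of power for the drug main effect and correct chance imbalance if it is prognostic beyond baseline cTnI. If it is not, adjustment costs almost nothing. The size rests wholly on the assumed prevalence of 30–50% and shift of 0.05–0.10 ng/mL.

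Three stronger conclusions that a reader might draw are not supported. The primary comparison is not biased. The sample size and stated power are not made wrong by the omission, since 152 reproduces without this factor. And precision is not shown to be lost, because no association is documented. Nor would the change rescue the cell-level comparisons named in section 2.1: at 33 per cell, power is about 21% for combination versus clopidogrel with RIPC (0.12 − 0.08 = 0.04) and 40% versus ticagrelor alone (0.14 − 0.08 = 0.06), a gap far beyond what one covariate can close.

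**What to change.** 1. Before any data are examined by allocation, amend section 12.2 to include prior clopidogrel (yes/no at first randomisation) as a fixed baseline covariate in the primary ANCOVA and in the pain and ST-deviation models. Define the variable explicitly: section 3.1 speaks of 3 to 7 days of treatment, while sections 5.4.2 and 6.2 refer to patients already on clopidogrel without an upper limit.
2. Reconcile section 4 with inclusion criterion 3 in section 4.1. Add indication as a second covariate only if both stable CAD and NSTEMI-ACS patients are enrolled.
3. Optionally, and only for patients not yet enrolled, keep separate envelope sets by prior clopidogrel for the drug randomisation.

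The cost is a few lines of text and about one degree of freedom per covariate, plus an extra envelope set if item 3 is adopted. No new data are needed. Fixing the choice in advance also avoids dispute over post hoc adjustment in a trial that section 5.3 describes as open label.
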